1.0 LIST OF ABBREVIATIONS/GLOSSARY OF TERMS

CI	Chief Investigator
CRF	Case Report Form
GCP	Good Clinical Practice
ISF	Investigator Site File
MDFT	Multidisciplinary Footcare Team
REC	Research Ethics Committee
RFL	Royal Free London NHS Foundation Trust
SOP	Standard Operating Procedure

3.0 STUDY SUMMARY

Official title:	Path Active; A multicentre randomised controlled trial
Brief title /Acronym:	PAM RCT
Sponsor reference number:	WWPP2.002
Public database trial ID:	TBC
Research Question	To evaluate the effectiveness of Path Active™ in people with diabetes who are at 'high risk' of foot ulceration.
Study design	Multicentre effectiveness randomised controlled trial
Eligibility criteria:	
Inclusion criteria:
 
 - Participant able to give informed consent. - Age >18 at the time of consent. - Diagnosis of Type 1 or Type 2 Diabetes. - Both Feet Intact (no ulceration). - Participant understands and is willing to participate and can comply with the follow-up regime. - Participant diabetes foot Risk Stratification as 'High Risk'. - Ability to walk independently for > 100 metres i.e without use of wheelchair, walking stick or personal assistance. - Participant able and willing to wear suitable footwear. - Must own a mobile phone and be willing to upload WWP app. 
Exclusion Criteria:
 
 - Either foot has less than 2 arterial vessel run-off on Doppler. - Poor visual acuity ie registered blind, unless supported by carer. - Current participation in another clinical investigation of a medical device or a drug; or participation in such a study within 30 days prior to study enrolment. - Body Mass Index (BMI) >40. - Active osteomyelitis (bone infection) suspected or diagnosed. - Active Charcot's neuroarthropathy. - Participant has bespoke contact insoles and footwear. - Participant is unable to use 'medium' or 'large' insoles due to foot size eg. small or extra large feet. - Participant has a pacemaker.

	- Participant is pregnant.
Anticipated start date	2 nd April 2024
Anticipated end date	31 st March 2025
Target number of participants	120
Primary aim(s)	The primary objective of this clinical investigation is to evaluate the effectiveness of Path Active™ in people with diabetes who are at 'high risk' of foot ulceration.
Secondary aim(s)	To establish the 'carbon footprint' of Path Active in different geographies.
Sources of funding	SBRI Healthcare Selection Panel. Ref SBRIH22P2006
Sponsor	Walk With Path

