5.2 RATIONALE

Foot ulceration and infection is a major factor leading to morbidity (amputation) and mortality. There are multiple comorbidities which can lead to foot ulceration and infection such as peripheral arterial disease and diabetes. The estimated cost of foot care in England for people with diabetes and foot ulceration alone is £1billion (Kerr 2019) with around 9000 amputations a year (one an hour). Many amputations occur due to ulceration leading to infection.

Path Active is an advanced at-home foot health monitoring system that combines unique patented, sensor-rich insoles and patient-adapted machine learning to prevent DFUs. Path Active does this by accurately mapping and measuring a person's foot pressure and temperature distribution to calculate increasing risk of foot ulceration and allow users to take appropriate actions to reduce their DFU risk. For patients, a highly-visual dedicated UI (User Interface - app & web portal), with embedded behavioural science-led 'nudge methodology', supports and encourages them to offload (rest) their feet to prevent DFU development and liaise remotely with their clinician. These systems have been shown to reduce DFU recurrence with the single modality of pressure measurement (Chatwin 2021; Abbott 2019). Additionally, Path Feel measures temperature change as a precursor to foot disease as well as pressure and reduces the need for frequency of clinic visits by providing at-home monitoring. Alerts are also captured on a clinical dashboard by the patient's clinical team which will alert them to potential foot problems and so they can contact the patient and provide rapid clinical care when required.

From a healthcare professional's perspective, the platform provides a major opportunity to save time and personalise care, focusing on only those patients who need help.

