8.0 PARTICIPANT SELECTION CRITERIA

Interested participants thought to be appropriate for the study will be approached by the local Community Foot Protection Team. Following informed consent, participants will be assigned a subject ID and their status checked that they satisfy inclusion and exclusion criteria prior to admitting them to the trial. Participants will be excluded if they do not satisfy inclusion and/or exclusion criteria.

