8.1 INCLUSION CRITERIA

- Participant able to give informed consent.
- Age >18 at the time of consent.
- Diagnosis of Type 1 or Type 2 Diabetes.
- Both Feet Intact (no ulceration).
- Participant understands and is willing to participate and can comply with the follow-up regime.
- Participant diabetes foot Risk Stratification as 'High Risk' as in Frame (2021) Scotland/England
<https://www.diabetesframe.org/>

- Ability to walk independently for > 100 metres i.e without use of wheelchair, walking stick or personal assistance.
- Participant able and willing to wear suitable footwear.
- Must own a mobile phone and be willing to upload WWP app.

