8.2 EXCLUSION CRITERIA

- Either foot has less than 2 arterial vessel run-off on Doppler.
- Poor visual acuity ie registered blind, unless supported by carer.
- Current participation in another clinical investigation of a medical device or a drug; or participation in such a study within 30 days prior to study enrolment.
- Body Mass Index (BMI) >40.
- Participant has bespoke contact insoles and footwear.
- Participant is unable to use 'medium' or 'large' insoles due to foot size eg. small or extra large feet.
- Participant has a pacemaker.
- Participant is pregnant.

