24.0 STATEMENT OF COMPLIANCE

The trial will be conducted in compliance with the protocol, Sponsor's Standard Operating Procedures (SOPs), GCP and the applicable regulatory requirement(s).

The study conduct shall comply with all relevant laws of the EU if directly applicable or of direct effect and all relevant laws and statutes of the UK country in which the study site is located including but not limited to, the Human Rights Act 1998, the Data Protection Act 1998, ICH GCP, the World Medical Association Declaration of Helsinki entitled 'Ethical Principles for Medical Research Involving Human Subjects' (2008 Version), the NHS Research Governance Framework for Health and Social Care (Version 2, April 2005).

This study will be conducted in compliance with the protocol approved by the REC and according to GCP standards. No deviation from the protocol will be implemented without the prior review and approval of the Sponsor and REC

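### The exclusion list in Section 3.0 contains active osteomyelitis and active Charcot's neuroarthropathy; the list in Section 8.2 contains neither, and nothing says which list governs.

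*Protocol*

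**What the plan says.** Section 3.0 (Study Summary) lists ten exclusion criteria. Two of them concern foot disease already present at entry: "Active osteomyelitis (bone infection) suspected or diagnosed" and "Active Charcot's neuroarthropathy".

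Section 8.2 (Exclusion Criteria) lists eight. After the body mass index limit it goes directly to "Participant has bespoke contact insoles and footwear". The two foot-disease items, which stand between those entries in Section 3.0, are absent there and from the rest of Section 8.2.

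Section 8.0 makes entry conditional on the criteria. Participants are to have "their status checked that they satisfy inclusion and exclusion criteria prior to admitting them to the trial". It does not say which of the two lists is meant.

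The closest inclusion criteria in Section 8.1 are "Both Feet Intact (no ulceration") and "Participant diabetes foot Risk Stratification as 'High Risk' as in Frame (2021) Scotland/England". Neither names osteomyelitis or Charcot foot.

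**The concern.** Eligibility should have one answer for each person screened. Here someone with active bone infection or active Charcot foot, and no ulcer, is excluded by one section and not excluded by name in the other. Three things follow.

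- **Compliance.** Section 24.0 states: "No deviation from the protocol will be implemented without the prior review and approval of the Sponsor and REC". The same enrolment would comply with Section 8.2 and deviate from Section 3.0, so a monitor could not classify it. The schedule in Section 10.2 marks eligibility confirmation at screening and again at the alert or concern visit, so the question can return after entry.
- **Safety.** Section 12.0.1 treats deterioration of existing medical problems as expected, and not reported unless related. Section 12.0.2 still records death, hospital admission and institutionalisation. Worsening of foot disease present at entry, short of those events, could go unreported.
- **Interpretation of alerts.** Section 5.2 says of the device: "Path Active does this by accurately mapping and measuring a person's foot pressure and temperature distribution to calculate increasing risk of foot ulceration". If foot disease present at entry alters those signals, some alerts would reflect that disease and not predict a new ulcer. This would reach the sensitivity and specificity analysis in Section 15.2.2 and the alert review in Section 15.1.2.

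**Working it through.** No formula applies. The check compares the lists item by item and then searches for anything that resolves the difference.

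**Step 1. Exclusion criteria, in the order of Section 3.0**

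| Item | Section 3.0 | Section 8.2 |
|---|---|---|
| Arterial run-off on Doppler | yes | yes |
| Visual acuity | yes | yes |
| Other investigational study | yes | yes |
| BMI limit | yes | yes |
| Active osteomyelitis | yes | **no** |
| Active Charcot's neuroarthropathy | yes | **no** |
| Bespoke insoles and footwear | yes | yes |
| Insole size | yes | yes |
| Pacemaker | yes | yes |
| Pregnancy | yes | yes |
| Total | 10 | 8 |

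Difference: 10 − 8 = 2. Items only in Section 8.2: 0. The eight shared items match in wording and order. Section 8.2 shows no redaction mark or break where the two items would stand, so a fault in reading the PDF is unlikely. Both lists are current text, not an amendment log.

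**Step 2. Inclusion criteria.** Section 3.0 has nine and Section 8.1 has nine. Eight are identical. The ninth, on risk stratification, differs only by the reference added in Section 8.1. The only criteria lost between summary and body are therefore the two exclusions.

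**Step 3. Does another criterion cover the gap?** The intact-feet criterion is qualified only as absence of ulceration. The criteria on walking more than 100 metres unaided and on wearing suitable footwear may remove some affected people, but they name neither condition. The high-risk criterion depends on an external definition that the protocol does not reproduce, so its effect is unknown. The pre-randomisation assessments in Section 7.1 include medical history, arterial Doppler and a neuropathy test. Medical history might reveal either condition, but no assessment is directed at them.

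**Step 4. Does any text rank the lists?** Section 8.0 refers to the criteria in general and Section 24.0 to the protocol in general. Neither condition is named outside Section 3.0, and no precedence rule was found.

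**Step 5. Consequence for one case.** Take a person with active Charcot foot and no ulcer who meets all nine inclusion criteria and none of the eight shared exclusions. Under Section 3.0 the person is excluded; under Section 8.2 the person is eligible.

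**The case against.** The strongest reply is that Section 8.2 omits the two items but does not permit them. Anyone who passes the longer list also passes the shorter one, so the two can be applied together, and Section 3.0 is part of the protocol with which sites must comply. On that reading both exclusions are in force and this is an omission between summary and body. The reading is possible, but the protocol does not state it, and a site working from the section headed as the exclusion criteria has no prompt to look elsewhere. The usual convention that the body governs its summary leads the opposite way. That two ordinary conventions give different answers is the problem.

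Other objections limit the size of the consequence, and they stand:

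- The high-risk definition is not reproduced, so people with either condition may already fall outside it. The affected group could be small or nil.
- Screening forms F01 to F05 and the flow chart were not available, nor were some front pages. The forms may already carry all ten items.
- The effect on alerts is conditional. No alert rule appears in the text, but the device manual in Appendix 1 is not shown and may contain one. The analysis concerned is secondary.
- Eligibility is confirmed before randomisation, so the ambiguity applies to both arms alike. No bias in the comparison of Path Active with control is claimed.
- Section 17.3 provides a form and a reporting route for deviations. That handles a mistaken enrolment afterwards; it does not settle whether there was one.

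**Conclusion.** The concern holds: the exclusion criteria are wrong as written, because two current sections give different lists. The size is exact as to text: 2 of the 10 exclusions in Section 3.0 are missing from Section 8.2, with no other criterion lost. The number of participants affected cannot be estimated, and divergence between the four sites is possible but not demonstrated.

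The textual finding rests on the two lists alone. The statement that nothing resolves it is limited to the text available. The consequence for enrolment assumes that a site screens from Section 8.2 as printed and that the high-risk definition does not itself remove such people. The consequence for alert accuracy further assumes that either condition alters the pressure or temperature signals, which the protocol does not establish. Because the difference concerns active foot disease in a trial of a foot device, it should be resolved before screening.

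**What to change.** The sponsor's clinical lead should confirm whether each of the two conditions is an exclusion. Section 3.0 and Section 8.2 should then carry one identical list, and the eligibility form should be checked against it before sites screen. The passages must be reconciled; this review takes no position on which list is right. A sentence naming the section that governs if summary and body differ would prevent a recurrence.

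The cost is about two lines of protocol text and a check of the eligibility form. If screening has already begun, participants already enrolled should also be checked against the reconciled list.

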4.0 STUDY FLOW CHART

5.0 INTRODUCTION

5.1 BACKGROUND

More than 4.9M people have been diagnosed with diabetes (DM) in the UK, and up to 25% (1.2M) will develop a Diabetic Foot Ulcer (DFU) in their lifetimes. 15-20% of DFUs lead to amputations which are followed by significantly increased mortality. The cost to taxpayers is enormous (Kerr 2019), consuming 1% of NHS budget annually.

The current method of providing periodic foot checks is inadequate, with the chance of recurrence of an ulcer being 40% in the first year, rising to almost 100% over 10 years (Armstrong 2017). Individuals at high risk of DFU go to clinic to have their feet checked at least once a month. This can be highly disruptive to their everyday lives. Furthermore, there is considerable environmental cost of patient travel and if a DFU occurs single-use consumables for treatment such as dressings, bandages, scalpels, blood tests, cultures for microbiology , etc.

5.2 RATIONALE

Foot ulceration and infection is a major factor leading to morbidity (amputation) and mortality. There are multiple comorbidities which can lead to foot ulceration and infection such as peripheral arterial disease and diabetes. The estimated cost of foot care in England for people with diabetes and foot ulceration alone is £1billion (Kerr 2019) with around 9000 amputations a year (one an hour). Many amputations occur due to ulceration leading to infection.

Path Active is an advanced at-home foot health monitoring system that combines unique patented, sensor-rich insoles and patient-adapted machine learning to prevent DFUs. Path Active does this by accurately mapping and measuring a person's foot pressure and temperature distribution to calculate increasing risk of foot ulceration and allow users to take appropriate actions to reduce their DFU risk. For patients, a highly-visual dedicated UI (User Interface - app & web portal), with embedded behavioural science-led 'nudge methodology', supports and encourages them to offload (rest) their feet to prevent DFU development and liaise remotely with their clinician. These systems have been shown to reduce DFU recurrence with the single modality of pressure measurement (Chatwin 2021; Abbott 2019). Additionally, Path Feel measures temperature change as a precursor to foot disease as well as pressure and reduces the need for frequency of clinic visits by providing at-home monitoring. Alerts are also captured on a clinical dashboard by the patient's clinical team which will alert them to potential foot problems and so they can contact the patient and provide rapid clinical care when required.

From a healthcare professional's perspective, the platform provides a major opportunity to save time and personalise care, focusing on only those patients who need help.

6.0 RESEARCH QUESTIONS

- Is Path Active as effective as regular routine podiatry review in foot ulcer prevention?
- Does using Path Active improve participant QoL?
- Are there any suggestions from participants to improve the device/app?
- Will preventing foot ulceration reduce NHSE carbon footprint?

6.1 PRIMARY AIM

The primary objective of this clinical investigation is to evaluate the effectiveness of Path Active™ in people with diabetes who are at 'high risk' of foot ulceration compared to regular routine podiatry clinical review.

6.2 SECONDARY AIMS

To model the carbon dioxide reduction that may occur if ulceration and the need for ulcer treatment is prevented, in differing UK geographies.

7.0 TRIAL DESIGN

7.1 METHOD

Study setting

Participants who have been assessed as having a 'high risk' of foot ulceration will be recruited from Community Foot Protection Teams in 4 sites across the UK. Participants will be recruited to the study to a maximum total of 120 (30 at each site) who have completed the study. The number of recruits required is based on a power calculation for the study at the 95% confidence interval.

The study is anticipated to run for 12 months.

Procedure

Potential participants will be approached to participate during routine review by the Community Foot Protection Teams and consented by them for the study. All participants will be screened at pre-assessment by the Community Foot Protection Teams.

Following completion of informed consent the participant will have;

- Medical History
- Arterial Doppler scan

- Test for Neuropathy
- Eligibility confirmation
- EuroQoL Assessment (EQ-5D-5L)
- Patient Questionnaire
- Randomised to 'Path Active Group' or 'Control Group' using computer randomisation.

If the participant is randomised to use the device in the 'Path Active Group';

- Participant Training in device and mobile app use (Appendix 1).

If there is an alert from Path Active app the participant will be asked to reduce walking and rest their feet. If the alert continues and activates the clinical dashboard, patients will be contacted to attend clinic for review.

If the participant is not randomised to use the device in the 'Control Group', they will continue with their regular podiatry clinical reviews with the Community Foot Protection Team who will provide their standard of care.

Day 84 (week 12). At the end of study;

- EuroQoL Assessment (EQ-5D-5L)
- Patient Questionnaire

If the participant is randomised to use the device;

- Device retained by clinical research team.

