10.2 SCHEDULE OF EVENTS

Path Active	Screening (Pre-enrolment assessment)	Active phase 0 - 84 days.			Final visit
Visit No:	1	2		3 due to alert/concern	4
Form Number	F01, F02, F03, F04, F05	F06	F06	F07 (F09)	F08
TIMING	Pre-Assessment	Day 0 Path Active Group	Day 0 Control Group	When required	Week 12 (Day 84)
Window of flexibility for timing of visits:	- 7 days			1 day	+7 days
Randomisation		Randomisation			
Informed Consent	X				
Medical History or change to medication	X			X	
Eligibility confirmation	X			X	
Feet Assessment Neuropathy	X				
Feet Assessment Vascular Doppler	X			X	
Adverse Events review (unless reported prior to visit)				X	X
Questionnaire		X	X		X

EQ-5D-5L		X	X		X
Path Active insole fitting		X			
Daily Dashboard Review by Clinical Team		X			

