11.0 ADVERSE AND SERIOUS ADVERSE EVENTS

11.1 GENERAL DEFINITIONS

An Adverse Event (AE) is any untoward medical occurrence in a patient or a clinical trial subject which does not necessarily have a causal relationship with the device/procedure.

A Serious Adverse Event (SAE) is an untoward occurrence that:

- Is fatal
- Is life threatening
- Requires hospitalisation or prolongation of existing hospitalisation
- Results in persistent or significant disability
- Consists of a congenital anomaly or birth defect
- Is otherwise considered medically significant by the Investigator

Medical and scientific judgement must be exercised in deciding whether an event is serious. There characteristics/consequences must be considered at the time of the event and do not refer to an event which hypothetically may have caused one of the above. All potential intervention-related AEs (such as falls and consequent injuries related to wearing the insoles) will be investigated and subject to expedited reporting to the REC.

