12.0 OPERATIONAL DEFINITIONS OF (S)AES

12.0.1 Expected (S)AEs - Not Reportable

This is a trial in a patient population with high levels of morbidity and co-morbid diseases and as such in this patient population, acute illness resulting in hospitalisation, new medical problems and deterioration of existing medical problems are expected.

In recognition of this, events fulfilling the definition of an adverse event or serious adverse events will not be reported in this study unless they are classified as 'related'.

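### The trial asks whether the device prevents foot ulcers, but the visible text schedules no foot inspection after screening in either arm, and the reporting rules do not fill the gap

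*Protocol*

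**What the plan says.** **The question.** Section 6.0 asks about foot ulcer prevention against routine podiatry review. Section 15.1.2 asks whether ulceration was prevented, and the carbon model in 15.1.1 depends on ulcers prevented. Section 15.2.1 compares effectiveness with standard podiatry review at Day 84. At entry, 8.1 requires "Both Feet Intact (no ulceration").

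**Follow-up (7.1).** Of controls it says: "they will continue with their regular podiatry clinical reviews with the Community Foot Protection Team". Of the device arm it says: "If the alert continues and activates the clinical dashboard, patients will be contacted to attend clinic for review". Whether device participants also keep their routine reviews is not stated. The Day 84 list there contains only the EQ-5D-5L and the patient questionnaire.

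**Schedule (10.2).** The neuropathy assessment is marked at screening only. The row "Feet Assessment Vascular Doppler" is marked at screening and at the as-required visit, headed "3 due to alert/concern". Eligibility is re-confirmed at that visit but not at Day 84. The row beginning "Adverse Events review (unless reported prior to visit" is marked at the as-required visit and at Day 84.

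**Reporting.** Section 11.1 defines adverse events broadly: "An Adverse Event (AE) is any untoward medical occurrence in a patient or a clinical trial subject". Section 12.0.1 then says that adverse events and serious adverse events "will not be reported in this study unless they are classified as 'related". Section 12.0.2 brings back three kinds of event: death, hospital admission and institutionalisation.

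**The concern.** A comparison of ulcer occurrence needs the feet of both arms to be looked at in the same way, at the same time, with the finding written down under the same rule. The visible text provides none of these. Clinic contact arises by different routes in the two arms: usual podiatry plus any concern for controls, and alerts plus any concern for device participants, whose routine reviews are left open.

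Two results are at stake. The first is the between-arm answer on ulcer prevention, and the carbon model that draws on it: a difference in the number of ulcers found could reflect how often feet were seen rather than how many ulcers formed. The second is the alert analysis in 15.2.2. Sensitivity and specificity both need to know who had an ulcer among those with no alert, and those are the device participants for whom no foot check after screening is stated.

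This is protocol content. Visits, examinations and recording rules are set here, and an analysis plan cannot recover ulcers that nobody looked for.

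**Working it through.** **Step 1. What each arm is scheduled to have after screening (7.1, 10.2, 12.2).**

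| Contact | Path Active arm | Control arm |
|---|---|---|
| Routine podiatry review | Not stated | Continues; no frequency or foot check fixed |
| Daily dashboard review | Yes | No |
| As-required visit | Through an alert or a concern | Through a concern |
| Foot assessment at that visit | Doppler | Doppler |
| Day 84 | Adverse event review, questionnaire, EQ-5D-5L | The same |
| Foot inspection at a fixed time | None listed | None listed |

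Doppler is a vascular test. Re-confirming eligibility at the as-required visit would check that the feet are intact, but only in people who attend it.

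**Step 2. Whether the adverse event review supplies the missing record.** A new ulcer meets the 11.1 definition of an adverse event. Under 12.0.1 it is not reported unless judged related. Under 12.0.2 an unrelated ulcer that leads to admission appears as an admission. An unrelated ulcer treated in the community falls under neither route, in either arm.

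**Step 3. Consequence for 15.2.2.** Sensitivity = true positives / (true positives + false negatives). Specificity = true negatives / (true negatives + false positives). False negatives and true negatives both come from device participants without an alert. With no stated foot check for them, an undetected ulcer is counted as a true negative, which inflates both measures.

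**Step 4. How much one ulcer matters (illustration).** The protocol gives no design event rate, effect size or power, so its total of 120 completers cannot be reproduced and is not tested here.

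Inputs:
- 120 completers (7.1). Equal allocation is assumed, giving 60 per arm.
- Annual ulcer risk of 20% to 40%. The 40% is the first-year recurrence figure in 5.1, used here as an assumed upper value. The 20% is an assumption with no source in the protocol.
- Constant hazard is assumed.

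Formula: 84-day risk = 1 − (1 − annual risk)^(84/365).

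| | 20% a year | 40% a year |
|---|---|---|
| 84-day risk | 1 − 0.80^(84/365) = 5.0% | 1 − 0.60^(84/365) = 11.1% |
| Ulcers per arm of 60 | 60 × 0.0501 = 3.0 | 60 × 0.1109 = 6.7 |
| Share of an arm's events in one missed ulcer | 1/3.0 = 33% | 1/6.65 = 15% |

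Each missed ulcer moves an arm's observed risk by 1/60 = 1.7 percentage points.

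**The case against.** **The unseen documents.** The flow chart (4.0) is not shown, nor are the forms for the as-required and Day 84 visits (F07 to F09), which may record ulcer status. Section 15.2.2 presupposes some reference record in the device arm. This stands as a limit on certainty. Even so, an ulcer field on a form would not establish that both arms are examined, or when and by whom.

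**Safety rules are not outcome rules.** Section 12.0.1 governs event reporting and does not forbid recording ulcers as an outcome. Section 12.2 also has all serious adverse events recorded and sent to the chief investigator, and an ulcer could be judged medically significant. This stands in part: it would be wrong to infer that no ulcer will be recorded. What the text lacks is a requirement to record them. Capture through 12.2 depends on individual judgement.

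**Controls can reach the as-required visit.** Correct. Section 12.2 names concern from either group, so the contrast between arms is less sharp than the alert pathway alone suggests.

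**Two stronger readings are tempting.**
- A reader might infer that the relatedness filter works against the device, since a control's ulcer cannot be related to an insole that person does not wear. But the filter applies to both arms. A device participant's ulcer from neuropathy or vascular disease is equally unrelated and equally dropped. The rule is asymmetric only for ulcers attributed to the insole.
- A reader might infer about three routine foot checks in controls against none with the device, by applying the monthly clinic visits described in 5.1 (84/30.4 = 2.8). That is background, not a study schedule, and nothing withdraws routine podiatry from the device arm. Section 5.2 does say the system reduces the need for frequent visits, so sites could reasonably differ, but silence is not evidence of fewer checks.

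**Sampling noise is larger.** With 60 per arm, the 95% half-width for a risk difference is 1.96 × √(2p(1 − p)/60), or 7.8 points at p = 0.0501 and 11.2 at p = 0.1109 (rough at so few events). One or two missed ulcers move the result by less. This is true, but the interval does not allow for unequal detection, so the two problems add.

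**Conclusion.** The point holds in limited form. On the visible text, no foot inspection is fixed after screening in either arm, an unrelated ulcer treated in the community need not be reported, and only controls are told that routine reviews continue. Followed as written, the trial has no assured like-for-like ulcer count and no assured reference status for device participants without an alert.

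The direction of any bias is unknown, and the documents do not support a claim that it favours either arm. Its size cannot be computed from the protocol. The illustration of about 3 to 7 ulcers per arm, with one missed ulcer worth 1.7 points or 33% to 15% of an arm's events, rests on assumed equal allocation, an assumed annual risk range and constant hazard. It shows only that the count is small enough for a few undetected ulcers to matter.

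Confidence is medium because the flow chart and forms are not shown. This is a cheap improvement, worth making before Day 84 data are collected.

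**What to change.** 1. In 7.1 and 10.2, add a brief foot inspection by the Community Foot Protection Team at the existing Day 84 visit, identical in both arms.
2. Record every new ulcer since randomisation, with its date, on the case report form as an outcome in both arms regardless of relatedness. State this as an explicit exception to 12.0.1. The date matters because an ulcer that formed and healed before Day 84 would not be seen at the inspection.
3. State in 7.1 and 10.2 whether routine podiatry reviews continue in the Path Active arm. The clinical choice is the sponsor's; the statement is needed so that sites act alike and readers know what was compared.

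Cost: a few minutes at each final visit, a few form fields and a protocol amendment, which under 24.0 needs Sponsor and REC approval. No new visit is required. If the unseen forms already hold an ulcer field, item 2 reduces to stating the rule in the protocol.
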